Title: Efficacy of bone marrow aspirate concentrate compared with platelet rich plasma for the treatment of symptomatic knee osteoarthritis: A randomized, controlled clinical trial

Principal Investigator: [name]

Co-Investigators: [name]

[name]

[name]

[name]

Funding Mechanism: Emcyte Corporation

Institution(s): Andrews Research and Education Foundation (AREF)
[name]
[name]
[contact]

Andrews Institute
[name]
[name]
[name]

1 Background / Scientific Rationale

In the United States it is estimated that 47 million people have been diagnosed with arthritis. 4.3 million have been diagnosed with isolated osteoarthritis of the knee and knee arthritis accounts for 20% of disability claims¹. Prevalence of the disease continues to climb and is expected to double by 2030. In addition 4 out of 5 patients with osteoarthritis have movement limitations¹. Currently there are no curative treatments for osteoarthritis. Surgical options include arthroscopy, osteotomies, and total joint replacement, but not all patients with knee osteoarthritis are candidates for surgical treatments, and others choose non-operative treatments instead of undergoing a procedure. Non-surgical treatment options include medications such as non-steroidal anti-inflammatory's (NSAIDs), injectables such as corticosteroids and visco-supplementation, or physical treatments such as rehabilitative therapy, unloading braces,

and activity modifications (i.e. canes or walkers). Additionally weight loss can help in the battle to reduce pain in cases of knee osteoarthritis.

The clinical efficacy of hyaluronic acid or corticosteroid injections has been reported, but effects are short lived. This has led to additional injection options such as autologous derived blood products which have been documented to alleviate symptoms related to knee osteoarthritis, with recent comparative studies suggesting a greater, long-lasting effect with these blood derived products like platelet rich plasma (PRP).²⁻⁸ Additionally some studies have suggested an increased positive effect with a combination of medications with PRP.⁹⁻¹²

While PRP shows promise in helping restore function to these patients, there are still concerns with PRP's long term outcomes. Another option that has become more popular for physicians treating this debilitation condition is bone marrow aspirate concentrate (BMA), which uses undifferentiated cells found in the bone marrow to promote healing and tissue

regeneration.¹³ These cells have the ability to replicate into a multiple different tissue types. With BMA, the marrow is concentrated provide better healing of the damaged tissue and aid in growth and repair. The full benefits of BMA are still unknown, but studies have shown the treatment can reduce swelling, relieve pain, and improve healing in articular cartilage and bone grafts.¹⁴

Autologous BMA has shown promising clinical potential as a therapeutic agent in regenerative medicine, including the treatment of osteoarthritis and cartilage defects,¹³⁻¹⁴ and the clinical efficacy platelet rich plasma has been documented to alleviate symptoms related to knee osteoarthritis.²⁻⁸ However, randomized, prospective comparison of the two techniques has not been reported in the literature and long term follow-up for both treatments is limited, and especially limited in the use of BMA for osteoarthritis treatment.

2 Objectives

The main objective of this study is to compare the effectiveness of bone marrow aspirate concentrate (BMC) to platelet rich plasma (PRP) injections for the treatment of knee osteoarthritis in regards to pain and function at multiple time points up to 24 months post injection.

3 Subject Eligibility

Patients between the ages of 18 and 80, with evidence of knee osteoarthritis will be screened for eligibility in the study. All subjects must present with pain or swelling of the knee of at least 4 months in duration and a Kellgren-Lawrence score between 1

and 3 upon x-ray evaluation. Potential subjects must be willing and able to provide informed consent and be willing and able to return for scheduled follow-up visits.

Exclusion criteria include: Patients with major mechanical axis deviation of more than 50% into either compartment (varus or valgus) or that have had a corticosteroid injection within 3 months or a hyaluronic acid injection within 6 months will not be eligible. Patients will be excluded if they have a history of the following medical conditions - diabetes, autoimmune disorders, disorders requiring immunosuppression, rheumatoid arthritis, hemophilic arthropathy, infectious arthritis, Charcot's knee, Paget's disease of the femur or tibia, or history of cancer. In addition anyone with an ongoing infectious disease or significant cardiovascular, renal or hepatic disease will be excluded.

4 Subject Enrollment

120 patients will be recruited through physician practices and with print, flyer or web based advertisements (AREF and EmCYTE websites). Those patients who contact the clinical trials department through the physician's office or by referral from an advertisement or otherwise will be prescreened for adherence to the inclusion and exclusion criteria via phone or in person.

Once the potential participant has been prescreened for inclusion and exclusion criteria, and agreed to be screened for participation in the study they will be instructed on study enrollment protocols which will include a visit with one of the physician investigators for evaluation, x-ray's and confirmation of adherence to the inclusion criteria. Subjects will also be instructed that they must not take any prescription or over the counter non-steroidal anti-inflammatory drugs (NSAIDS) for 3 weeks prior to the evaluation appointment. Following the physician evaluation and confirmation subjects will again have all study requirements explained to them and go through the described informed consent process. The subject will then be randomly placed in one of the two study groups and be scheduled to receive either a PRP injection or BMC injection in their affected knee.

5 Study Design and Procedures

Upon enrollment and completion of the informed consent process, patients will be randomized into the 2 study groups of 60 each, based on a list compiled by a random number generator prior to initiation of the study. Both Groups will complete the Western Ontario and McMaster Universities Osteoarthritis Index (WOMAC), and the Subjective International Knee Documentation Committee Subjective Score (IKDC) questionnaires prior to any treatment. Due to the invasive nature of obtaining marrow aspirate blinding of the subjects and clinicians will not be performed. Group 1 [PRP]: Will receive a single (1) intra-articular injection of PRP. Group 2 [BMC]: Will receive a single (1) intra-articular injection of BMC after obtaining informed consent. Both types of injections and all associated procedures will be performed in the clinic or lab setting with local anesthesia. Following the injection patients will be asked to complete a short questionnaire documenting the BMC or PRP collection, preparation and injection experience. Ten patients will be randomly selected from both (20 total subjects) the PRP and

BMC groups to have analysis performed on the BMC and PRP as described below. This analysis will not be performed on patients not randomly selected. In patients randomly selected after the BMC or PRP have been prepared for injection, a small sample (1 mL) of the BMC or PRP will be separated and sent to an independent lab (Biosciences Research Associates, Inc) for analysis. The PRP will be analyzed with a CBC and the BMC will be analyzed for TNC, human CD34+ hematopoietic stem/progenitor cell assay, CFU-F, plasma free hemoglobin, cell viability percent, and hemolysis percent. Evaluation, a 4 view x-ray series (long leg, lateral, sunrise, and bilateral Rosenberg), and injections will be provided at no charge to the patients. Patients will then be given standard follow-up care instructions that include no use of NSAIDS for at least 7 days and partial weight bearing on the limb for 2-3 days, followed by the initiation of a standard physical therapy program at one week following injection.

After the injection subjects will be required to complete the WOMAC and IKDC questionnaires as well as report any medications they are using via email or phone (paper method will be available on request) at 1, 3, 6, 9, 12, 18, and 24 months following the injection.

PRP protocols

All subjects who will receive a PRP injection will be treated under the normal standards of care for such a treatment. These procedures include drawing of blood from the patient using a standard aseptic technique (step by step instructions found in appendix A - Technique Manual) into a syringe with anticoagulant (see appendix B – MSDS sodium citrate USP). From the syringe of patients randomly selected for analysis 1 mL of blood will be separated and sent to a lab for analysis. The remaining blood in the case of patients randomly selected or all of the blood in those not randomly selected will then be placed into a single concentrating device and placed in a centrifuge for 1.5 minutes at 3800 RPM which will separate the red blood cells from the plasma and platelets (see appendix C – centrifuge Op Manual). The plasma and platelets will then be separated off with a syringe and re-spun for 5 minutes at 3800 RPM in the centrifuge to separate the platelets from the plasma. The platelets will then be separated off for injection into the patient's knee (step by step instructions found in appendix A - Technique Manual). The PRP preparation procedure results in 7 mL of product in patients randomly selected for analysis 1 mL will be separated and sent to a lab for analysis leaving 6 mL for injection. Both the 1 mL of blood and the 1 mL of PRP of patients randomly selected for analysis will be sent to an independent lab (Biosciences Research Associates, Inc) to undergo analysis for CBC. The treating physician will then inject the PRP into the affected knee joint following standard aseptic technique per the physician's normal standard of care. The above mentioned processes will be performed using the EmCyte GenesisCS Component Concentrating System Pure PRP® II-60 mL 2015kit (product number (GS60-PURE-II) (EmCyte Corporation, Fort Myers, Florida) which has been approved by the FDA for use in PRP treatments (see Appendix D – FDA letter). This entire process will be completed in a single patient visit. Any unused portion of a sample in the physician's office will be disposed of through standard biohazard waste disposal systems as required by law.

BMA Protocols

Subjects who receive a BMA injection will again be treated under the normal standards of care for such a treatment. These procedures include a bone marrow harvest from the posterior iliac

crest using a prone and posterior approach. The trocar will be rinsed with 15 mL of heparin (see MSDS heparin). A total of 50 mL of bone marrow will be drawn into a syringe containing 10 mL of anticoagulant (see appendix B – MSDS sodium citrateUSP). The filter will be rinsed with 3 mL of heparin. The bone marrow will then be filtered. From the syringe with filtered bone marrow, for patients randomly selected for analysis, 1 mL of filtered BMA will be separated and sent to a lab for analysis. The remaining bone marrow will be separated into a single concentrating device, counterbalanced and placed in a centrifuge for 2.5 minutes at 3800 RPM for separation of the bone marrow concentrate. The plasma and cell concentrate will then be separated off with a syringe and stopcock, then transferred into the concentrating accessory, counterbalanced and re-spun for 7 minutes at 3800 RPM in the centrifuge to separate the cell concentrate from the plasma. After the plasma is drawn off and swirled to resuspend, the BMC will be drawn into a syringe for injection into the patient's knee (step by step instructions found in appendix A - Technique Manual). The BMC production procedure results in 7 mL of product for patients randomly selected for analysis 1 mL will be separated and sent to a lab for analysis. Both the 1 mL of BMA and the 1 mL of BMC of patients randomly selected for analysis will be sent to an independent lab (Biosciences Research Associates, Inc) to undergo analysis for TNC, human CD34+ hematopoietic stem/progenitor cell assay and CFU-F, plasma free hemoglobin, cell viability percent, and hemolysis percent.. This sample will be packaged in the company's standard sample packaging and shipped per instructions (see appendix F – BSR Quality Evaluation Program Specimen Preparation Kit) for delivery to the lab to undergo verification testing. The treating physician will then inject the BMC into the affected knee joint following standard aseptic technique per the physician's normal standard of care. The above mentioned processes will be performed using the EmCyte GenesisCS Pure BMC®-60 ml 2015kit (product number BC60-PURE) (EmCyte Corporation, Fort Myers, Florida) which has been approved by the FDA for use BMC treatments (see Appendix E – FDA Letter). This entire process will be completed in a single patient visit. Any unused portion of a sample in the physician's office or in the lab will be disposed of through standard biohazard waste disposal systems as required by law.

6 Expected Risks and Benefits

Risks and Discomforts: Potential risks include those expected with any injection including syncope, dizziness, headache, nausea, tachycardia, infection (septic arthritis, phlebitis, and osteomyelitis), bleeding, or pain. Additionally the patient may experience knee stiffness or inflammation associated with the procedures. For BMA harvest, there is the potential for pain, bleeding or infection at the harvest site, as well as the possibility of retroperitoneal hematoma. The filter and the trocar from the bone marrow aspiration kit will be rinsed with heparin. Risks with the use of heparin include hypersensitivity, hemorrhaging, heparin-induced thrombocytopenia (HIT), heparin-induced thrombocytopenia and thrombosis (HITT), and delayed onset HIT and HITT. As with any research involving patients there is the inherent risk of a breach in patient confidentiality though this will be minimized through the use of subject code numbers and adherence to all HIPAA guidelines.

Benefits: Direct benefits of the study include a physician visit, x-rays and an injection of BMA and/or PRP at no cost, as well as potential pain relief, improvement of knee function, and improvement of quality of life, which all could lead to the avoidance of surgical intervention. It is also believed that the information obtained in this study will help advance treatment of osteoarthritis through the use of regenerative medicine.

7 Data Management Procedures

All personal information is strictly confidential and no names will be disclosed except as required by law. All research information will be managed and accessible by only the named investigators and their medical staff. Data sheets will have names and identifying information replaced with a subject code to protect the confidentiality of the subject. All information provided by the subject during this project will be recorded on the appropriate forms and stored in a locked room in the AREF research facility. In addition all subject data forms will be scanned and stored, along with summary information forms, spreadsheets, and photos, in a secure password protected folder on a laptop in which only study investigators will have access to, and will be permanently deleted following any and all publications or presentations have been completed related to this research. All records related to this research will be retained in a secure location for a period of 3 years following the completion of all study related activities, at which time they will be properly destroyed.

8 Data Analysis

All data will be entered into an excel spreadsheet for analysis that will include obtaining standard measures such as means and standard deviation. Data will be analyzed as scores on the two questionnaires as well as across subsets of the individual questionnaires for function, quality of life and pain scores. Additional determinations based on medication usage and failure rates will be examined as well.

9 Statistical Considerations

A power analysis was performed to determine sample size based upon recent clinical trials comparing PRP to HA for the treatment of osteoarthritis. Analysis utilized the average of standard deviation to detect average of group mean effect at 80% power. This determined that 25 patients per group would be needed to reach statistical significance with the WOMAC and that 50 patients would be needed per group for the IKDC. Considering a potential dropout rate of 20%, 60 patients per group was chosen as the sample size.

Data will be analyzed for differences between groups using a repeated measures ANOVA design, using a significant p-value of < 0.05 for rejecting the null hypothesis. Additional subjective analysis will be performed on data involving the patient experience with regards to the injection.

10 Quality Control and Assurance

All protocols will be monitored and analyzed data will be checked for accuracy by the principal investigator and/or a designated AREF research team member. All medical data will be kept in compliance with HIPAA guidelines.

11 Regulatory Requirements

Informed Consent:

The informed consent process will be performed by a study coordinator from the Andrews Research and Education Foundation. All subjects will have the study described to them and will be given as much time as they would like to read an approved, stamped version of the informed consent document. After signing the informed consent document, they will be given a copy for their records.

Subject Confidentiality:

Subject confidentiality information is listed above in #7 (Data Management Procedures). All medical data will be recorded and stored in compliance with HIPAA guidelines.

12 References

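### The BMC procedure uses heparin, but section 3 does not exclude known heparin hypersensitivity or prior HIT/HITT (cheap improvement for patient safety)

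*Combined protocol and SAP*

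**What the plan says.** **Exposure.** Under the BMA protocols in section 5, the trocar is rinsed with 15 mL of heparin. After the marrow is drawn, the filter is rinsed with 3 mL and the marrow is passed through it. Both steps are stated without exception. The PRP procedure, as described, uses sodium citrate and involves neither heparin nor a marrow harvest.

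**Named risks.** Section 6 attributes hypersensitivity, haemorrhage, HIT, HITT and their delayed-onset forms to heparin. It attributes pain, infection, bleeding and possible retroperitoneal hematoma to the harvest.

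**Eligibility.** The excluded histories in section 3 are "diabetes, autoimmune disorders, disorders requiring immunosuppression, rheumatoid arthritis, hemophilic arthropathy, infectious arthritis, Charcot's knee, Paget's disease of the femur or tibia", followed by cancer. The section adds that "anyone with an ongoing infectious disease or significant cardiovascular, renal or hepatic disease will be excluded". It also excludes major axis deviation and recent corticosteroid or hyaluronic acid injections. Heparin, HIT and HITT do not appear.

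**Order of events.** In section 4, candidates are "prescreened for adherence to the inclusion and exclusion criteria via phone or in person". They then have "a visit with one of the physician investigators for evaluation, x-ray's and confirmation of adherence to the inclusion criteria", before which "they must not take any prescription or over the counter non-steroidal anti-inflammatory drugs (NSAIDS) for 3 weeks prior to the evaluation appointment". Consent follows, and "The subject will then be randomly placed in one of the two study groups". Section 5 sets the allocation: "patients will be randomized into the 2 study groups of 60 each".

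**The concern.** Section 6 recognises a hazard that section 3 does not screen for. In a two-arm comparison, each patient should be able to receive either treatment before the allocation is made. Here one arm carries a specific contraindication that the eligibility rules do not mention.

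Two things could follow for an affected patient allocated to BMC:

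- **The harvest goes ahead.** The patient is exposed to a risk that the plan itself lists. This is the main issue, and it concerns safety.
- **The harvest is declined after allocation.** The patient is then untreated, withdrawn or switched. A patient with the same history allocated to PRP would be treated normally, so this loss can arise in only one arm. Sections 8 and 9 give no rule for analysing a patient who was allocated but not treated as assigned.

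**Working it through.** The point rests on the text. The plan gives no figure here to reproduce.

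**Step 1: is heparin part of every BMC treatment as written?** Yes. Both rinses (15 mL for the trocar, 3 mL for the filter) are stated without condition. The filter rinse belongs to marrow processing rather than to the draw. The heparin concentration and the amount that reaches the patient are not given, so the dose cannot be judged.

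**Step 2: does any written criterion catch a known heparin contraindication?**

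| Section 3 item | Covers heparin hypersensitivity or HIT/HITT? |
|---|---|
| Hemophilic arthropathy | No; it concerns joint disease in a bleeding disorder |
| Autoimmune disorders | Not as a stated rule; it may catch some immune platelet disorders |
| Significant cardiovascular, renal or hepatic disease | No; it overlaps only with general procedural risk |
| Corticosteroid and hyaluronic acid washouts | No |
| Remaining items | No |

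**Step 3: does any step before randomisation require the check?** Section 4 does not name it. Prescreening is against the written criteria, which lack it. The physician visit includes an evaluation, but its content is not specified. The medication reporting in section 5 cannot serve as a screen because it comes later: "After the injection subjects will be required to complete the WOMAC and IKDC questionnaires as well as report any medications they are using", at 1 to 24 months.

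**Step 4: how many patients might this involve?** The documents give no prevalence. Let p be the assumed proportion of otherwise eligible patients with such a history, with 60 patients in BMC. The expected number in BMC is 60 × p, and the chance of at least one is 1 − (1 − p)^60.

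| Assumed p | Expected in BMC | Chance of at least one |
|---|---|---|
| 0 | 0 | 0 |
| 0.1% | 60 × 0.001 = 0.06 | 1 − 0.999^60 = 5.8% |
| 0.5% | 60 × 0.005 = 0.3 | 1 − 0.995^60 = 26% |
| 1% | 60 × 0.01 = 0.6 | 1 − 0.99^60 = 45% |
| 2% | 60 × 0.02 = 1.2 | 1 − 0.98^60 = 70% |

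These rows assume that nobody is stopped informally at the physician visit, so they are upper figures for each p. For scale, section 9 needs 50 per group for the IKDC and enrols 60, a margin of 60 − 50 = 10. Even the last row costs about one patient.

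**The case against.** The best defence is that safeguards already exist. The section 3 list is introduced as inclusive rather than exhaustive. A physician investigator evaluates every candidate before randomisation, and checking for the listed histories already means taking a medical history. BMA treatment is placed under normal standards of care, which would ordinarily include an allergy check. The technique manual, the heparin safety sheet and the consent pages were not available for this review and may carry a warning. All of this is fair, and it makes actual exposure unlikely. It does not supply a written rule that acts before allocation. The standard-of-care wording applies to subjects who receive the BMA injection, so it may prevent harm but not loss from one arm.

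The documents do not support three stronger readings that a reader might infer:

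- **That the plan controls no medication before randomisation except NSAIDs.** Section 3 also bars a corticosteroid injection within 3 months and a hyaluronic acid injection within 6 months.
- **That the plan is deficient because it requires no recorded fitness for marrow harvest and no anticoagulant history.** Section 6 names harvest bleeding and retroperitoneal hematoma, but not anticoagulant use or bleeding disorders as risk factors. The need for that history is a clinical inference, and recording it is largely a documentation preference. It is therefore secondary.
- **That the trial's power or error rates are threatened.** Nothing in the documents suggests numbers large enough for that.

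**Conclusion.** The concern holds in a narrow form. Section 3 as printed does not exclude patients with known heparin hypersensitivity or prior HIT/HITT, although the BMC procedure uses heparin and section 6 names these reactions as risks. Such a patient meets the written criteria and can be allocated to BMC.

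The practical size is unknown, probably very small and possibly zero. The illustrative figures rest wholly on an assumed prevalence and ignore informal screening. The conclusion concerns the eligibility and enrolment sections as printed; unseen appendices could reduce the practical risk further. This is a cheap improvement for patient safety, with avoidance of loss from one arm as a minor second benefit.

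**What to change.** Add to the section 3 exclusions: known heparin hypersensitivity, or a history of HIT or HITT. In section 4, state that this is checked at the existing prescreen and confirmed at the physician visit, before randomisation. Apply it to all candidates, since the arm is not yet known.

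Optionally, ask about bleeding history and current anticoagulant use at the same visit, because harvest bleeding and retroperitoneal hematoma are named risks.

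The cost is amendment wording and a few questions at contacts that already take place, with no new visit or test. The downside is that a few otherwise eligible patients, including some who would have been allocated to PRP, are screened out.

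### Baseline WOMAC and IKDC may be scored after an unblinded patient knows the assigned arm, because the only time limit is that they precede treatment

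*Combined protocol and SAP*

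**What the plan says.** Section 4 (Subject Enrollment) runs in this order: physician evaluation with x-rays and eligibility check, consent, then allocation and booking: "The subject will then be randomly placed in one of the two study groups and be scheduled to receive either a PRP injection" or a BMC injection. No questionnaire is listed at the evaluation visit.

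Section 5 (Study Design and Procedures) repeats the step from consent to randomisation: "Upon enrollment and completion of the informed consent process, patients will be randomized into the 2 study groups of 60 each". It next says that both groups complete the WOMAC and the "Subjective Score (IKDC) questionnaires prior to any treatment". On masking it says that "blinding of the subjects and clinicians will not be performed", giving the invasiveness of the marrow harvest as the reason. Follow-up questionnaires are due "at 1, 3, 6, 9, 12, 18, and 24 months following the injection".

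Of collection, preparation and injection, the PRP part of section 5 says: "This entire process will be completed in a single patient visit". The BMA part says the same. Section 9 (Statistical Considerations) names a repeated measures ANOVA for differences between groups at p < 0.05. It does not say whether or how baseline is used.

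**The concern.** WOMAC and IKDC are patient-reported and are the trial's efficacy instruments. A patient who has been allocated and booked for a named injection can know the arm before filling in the baseline forms. One arm involves a marrow harvest and the other a blood draw, so a reaction to the assignment could plausibly differ between arms.

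A baseline scored after disclosure is a post-randomisation measurement, and randomisation no longer protects it. If it serves as a time level, a change reference or a covariate, that reaction enters the treatment comparison. No later analysis can reconstruct what the patient would have scored without knowing the arm.

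**Working it through.** **Order of events.** The plan gives no figure to reproduce here, so the first check is to set the statements side by side.

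| Event | Where | Timing stated |
|---|---|---|
| Evaluation, x-rays, eligibility | Section 4 | Before consent; no WOMAC or IKDC listed |
| Consent | Sections 4, 5, 11 | Before randomisation |
| Randomisation | Sections 4, 5 | After consent |
| Booking of PRP or BMC injection | Section 4 | With or after randomisation |
| Baseline WOMAC and IKDC | Section 5 | Before treatment; nothing else |
| Collection to injection | Section 5, PRP and BMA parts | One visit |

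Forms completed at the consent contact would comply. So would forms completed at the start of the injection visit with the arm known. Section 5 is not strictly chronological, so sentence order does not prove a post-allocation baseline. No visible sentence rules one out.

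**Size, as illustration only.** Assumptions, none of them from the documents: baseline is one of T = 8 time points (baseline plus the seven follow-ups), SD 1, compound symmetry with correlation ρ, no true difference, and a shift of s SD in one arm. The n = 50 analysed per group is also assumed; it equals the section 9 IKDC requirement before dropout.

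*A. Shift at baseline only.*
- Main effect: bias s/8; SD of a patient's mean √((1+7ρ)/8) = 0.75 at ρ = 0.5; standard error 0.75 × √(2/50) = 0.15. The noncentrality is (s/8)/0.15 = 0.083, 0.167, 0.250 for s = 0.1, 0.2, 0.3. The noncentral t with 98 df gives 5.1%, 5.3%, 5.7%.
- Group-by-time: F with 7 and 686 df, λ = 2n(s²/4)(7/8)/(1−ρ) = 0.4375, 1.75, 3.9375 at ρ = 0.5. Result: 6.6%, 12.4%, 24.6%.
- Over s = 0.1 to 0.3, group-by-time is 6.1% to 18.0% at ρ = 0.3 and 7.8% to 40.9% at ρ = 0.7. The main effect is at most 6.0%.
- A simulation of 20,000 trials at ρ = 0.5 gave main effect 5.2%, 5.3%, 5.6% and group-by-time 6.3%, 12.7%, 24.4%. With s = 0 it gave 4.8% and 5.0%.

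*B. Same shift at all eight time points, ρ = 0.5.* The main effect (bias s) is 10.1%, 26.2%, 50.8%. Group-by-time stays at 5.0%.

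*C. Clean baseline, shift at the seven follow-ups, ρ = 0.5.* The main effect (bias 7s/8) is 8.9%, 21.1%, 41.0%. Group-by-time is 6.6%, 12.4%, 24.6%.

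*Single follow-up, baseline-only shift, ρ = 0.5, normal approximation.*
- Change from baseline: bias s, standard error √(2(1−ρ)) × √(2/50) = 0.20; false-positive rate 7.9%, 17.0%, 32.3%.
- Baseline-adjusted comparison: bias ρs, standard error √(1−ρ²) × √(2/50) = 0.173; 6.0%, 8.9%, 13.9%.

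**The case against.** The strongest reply is that the plan is silent rather than wrong, and that harm needs several conditions: the forms are given after disclosure, knowing the arm changes the answers, the change differs between two active arms, and baseline enters the analysis. The objective speaks of time points after injection. A comparison of the seven follow-up scores alone would be valid under randomisation as far as baseline is concerned, at some cost in precision. The main effect, a natural reading of differences between groups, barely moves in scenario A. If a reporting shift persists equally throughout, a clean baseline lowers the main-effect error (50.8% to 41.0% at s = 0.3) but raises the group-by-time error (5.0% to 24.6%). Unblinded follow-up is the larger exposure, and the plan accepts it with a reason.

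Most of this stands, and it limits the weight of the point. It does not remove it. Section 9 leaves the role of baseline open, so none of the affected analyses is excluded. The reason given for not blinding does not require baseline to follow disclosure. Cancellation of equal shifts cannot be relied on, since the documents give no basis for expecting it; equally, they give none for the baseline-only shift in scenario A.

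**Conclusion.** The concern holds as a minor point. The visible text permits baseline scoring after the arm is known and nowhere places it before allocation or disclosure. It does not show that baseline will be collected that way. It also does not say when patients learn their arm; that they can know it beforehand follows from the lack of blinding and the booking of a named injection.

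The size in this trial is unknown. The calculated rates rest wholly on the assumed shift, correlation and covariance. They show that the consequence can range from negligible to material, depending on how baseline is used and whether the shift persists. They are not evidence of bias in this trial. Fixing the order removes the bias that arises at baseline, not the bias from open-label reporting later.

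**What to change.** Amend sections 4 and 5 to state that WOMAC and IKDC are completed after consent and before the allocation is drawn or disclosed. Record the date and time of the questionnaires, the allocation and the injection. Use that pre-allocation record as the baseline for every randomised patient.

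The cost is low. Section 11 says: "The informed consent process will be performed by a study coordinator". The same two forms can be completed at that contact, with no new instrument, visit or change in sample size. The downside is a somewhat longer gap between baseline and injection, of a length the documents do not give; the recorded dates will show it. The timing also fits the NSAID-free period in section 4, which is set "for 3 weeks prior to the evaluation appointment", the step before consent.
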